6.3 Safety population

All randomized patients who have started treatment with long-term oxygen therapy (LTOT) belong to the *Safety population* and will be studied with regard to adverse events. If there are no incorrectly randomized patients or patients who started the wrong treatment, the safety population will be the same as the ITT population.

6.4 Subpopulations

Primary analysis:

- I. All randomized participants

Secondary analyses:

- II. Participants with more severe resting hypoxemia ($\text{PaO}_2 < 7.4 \text{ kPa}$ on air) at LTOT start
- III. Participants with more moderate hypoxemia ($\text{PaO}_2 7.4\text{--}8.0 \text{ kPa}$ on air) at LTOT start
- IV. Participants with verified COPD (COPD as primary diagnosis and $\text{FEV}_1/\text{FVC} < 0.7$ after bronchodilation) [defined using primary diagnosis + spirometry in Swedevox]
- V. Participants with primary diagnosis other than COPD

7 Statistical analysis

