4.2 Outcome variables

The outcome variables that will be analyzed and reported at UCR are underlined. This will be performed in the subgroups stated in Section 6.4. The secondary outcome variables that are not underlined will be analyzed later by the sponsor Region Blekinge with methods outlined in this SAP.

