9.1 Limit of non-superiority and Hypotheses

A time-to-composite event survival analysis, with composite event equal to death or 1st hospitalization as endpoint, is used. The hypothesis of non-superiority of continuous oxygen is tested. The null hypothesis is rejected if the hazard ratio (HR) of continuous oxygen vs. 15h/day exceeds the limit 0.67. The use of oxygen is burdensome and with hospitalization, being less serious than death, incorporated into the primary endpoint, the HR of 0.67 was judged to be the appropriate limit for the composite primary outcome. This was the difference in mortality or hospitalization that the investigators judged to be clinically worthwhile. (See also section 10 Changes to the planned analysis.)

$H_0: HR_{24h/day} \leq 0.67$

$H_A: HR_{24h/day} > 0.67$ Continuous oxygen is not better than 15h/day;

If significance is obtained, the conclusion is that LTOT prescribed for 24 h/day does not reduce the rate of the composite event of all-cause death or 1st hospitalization at 1 year compared to LTOT prescribed for 15 h/day in patients starting LTOT for chronic respiratory failure.

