9.2 Sample size calculation

Calculation of the final required sample was based on a time-to-composite event survival model with the use of the Cox proportional hazards (PH) model and checked against the results of the log-rank test statistic. Assuming 80% power to verify a hazard ratio for death or 1st hospitalization of more than 0.67 in the 24h group vs. the 15h group, a one-sided type I error rate of 0.05, and an event rate of 80% based on Swedevox registry data, we calculated a total sample size of 189 patients with Cox PH and 181 using the log-rank statistic. Making allowances for a loss of patients in the PP analysis, the final planned total trial size is 230, with 1:1 allocation. No patient is expected to be lost to follow-up for the primary composite endpoint of death or 1st hospitalization in the ITT population, due to the use of national registries. The following R code for a Cox PH non-inferiority calculation, inverting the hypothesized hazard ratio from the non-superiority hypothesis for this study, was used for the sample size calculation:

#Hazard Ratio, hr

#Null-Hypothesis Hazard Ratio, hr0

#Overall Probability of Event, pE

#Proportion of Sample in Group 'A', pA

```
> hr=1
```

```
> hr0=1.5
```

```
> pE=0.8
```

```
> pA=0.5
```

```
> alpha=0.05 # 1-sided test
```

```
> beta=0.20
```

```
> (n=((qnorm(1-alpha)+qnorm(1-beta))/(log(hr)-log(hr0)))^2/(pA*(1-pA)*pE))
```

```
[1] 188.0317
```

```
> ceiling(n)
```

```
[1] 189
```

10 Changes to the planned analysis (2020-01-22)

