[figure not shown]
[figure not shown]

Figure 3 Cumulative hazard by treatment

Figure 3.1 Primary outcome (ITT)

[figure not shown]
Similar figures will be constructed for all primary and secondary outcomes (at 3 months and 1 year) presented by ITT, PP, Subgroups 1-4.

Figure 4 Kaplan-Meier figures

Kaplan-Meier figures will also be presented for all primary and secondary outcomes

Figure 5 HR with non-superiority limit for the primary endpoint

90% confidence intervals for HR_{24hvs.15h}, for the ITT, PP and subgroup populations. The p-value corresponds to the one-sided test, at 5% significance level, that the lower limit exceeds the hypothesized value 0.67.

Similar figures will be created for all secondary endpoints

3 Listings

[Listing 1](#) Patient disposition

[Listing 2](#) Demographics and characteristics at screening visit

Participant characteristics should also include center, population and randomized treatment group.

[Listing 3](#) Time of randomization to death or censoring

[Listing 4](#) Patients withdrawal

[Listing 5](#) Patients discontinuing LTOT

[Listing 6](#) Time of randomization to hospitalization or censoring

[Listing 7](#) Subjects excluded from the ITT and PP

[Listing 8](#) Screening failures

[Listing 9](#) Adverse events

[Listing 10](#) Loss to follow-up for the composite endpoint of death or 1st hospitalization

[Listing 11](#) Study termination (End of study)

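### Each subgroup gets its own test against 0.67 and no treatment-by-subgroup interaction is planned, so differing subgroup results could not be read as a different effect

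*SAP*

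**What the plan says.** Section 6.4 makes all randomized participants the primary analysis and lists four secondary subpopulations in two pairs. The first pair is "Participants with more severe resting hypoxemia" (PaO2 on air below 7.4 kPa) and moderate hypoxemia (7.4 to 8.0 kPa). The second is spirometry-verified COPD and "Participants with primary diagnosis other than COPD". Section 4.2 says of the outcomes reported by the trial statistician: "This will be performed in the subgroups stated in Section 6.4".

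Section 9.1 gives the decision rule: "The null hypothesis is rejected if the hazard ratio (HR) of continuous oxygen vs. 15h/day exceeds the limit 0.67". Appendix 2, Figure 5 (numbered as in the body of the shells), shows 90% confidence intervals for the primary endpoint "for the ITT, PP and subgroup populations". Its caption attaches the one-sided 5% test against 0.67, and like figures are planned for the secondary endpoints. Tables 11.3 to 11.6 carry the Table 11.1 layout, with its two p-value columns, into each subgroup.

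Sections 7.5 and 7.6 and the shells contain no treatment-by-subgroup term. The correlational analyses in section 7.6 look for factors that predict outcome, which is prognosis and not effect modification. The SAP gives no expected size or power for any subgroup and no rule for reading subgroup results that differ.

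**The concern.** Pairing severe with moderate hypoxemia, and COPD with other diagnoses, asks whether the effect of 24 h/day depends on severity or diagnosis. Two separate tests against a fixed limit do not answer that. Each asks whether its own subgroup has enough events, and a favorable enough estimate, to exclude 0.67. One member of a pair can exclude it and the other not, simply because the trial was sized for the whole population.

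At stake is how a split result is interpreted. Section 10 records that the primary analysis was originally confined to COPD patients, so the COPD contrast is likely to draw attention.

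**Working it through.** **Inputs.** Section 9.2 gives "a one-sided type I error rate of 0.05, and an event rate of 80% based on Swedevox registry data", "Assuming 80% power to verify a hazard ratio for death or 1st hospitalization of more than 0.67", and "the final planned total trial size is 230, with 1:1 allocation". The code there uses a true HR of 1 and a limit of 1.5, the rounded inverse of 0.67. The SAP gives no subgroup sizes, so splits from 50/50 to 80/20 are an assumption.

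**The plan's own figure.** n = ((1.645 + 0.842)/ln 1.5)² / (0.25 × 0.8) = 188.03, rounded up to 189. This reproduces the SAP. Using 0.67 itself gives 193.

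**Chance that a group excludes 0.67.** With E events, P = Φ(√(E/4) × ln(true HR/0.67) − 1.645). At HR 1, ln(1/0.67) = 0.4005. The whole trial has 230 × 0.8 = 184 events: √46 × 0.4005 − 1.645 = 1.07, so P = 85.8%.

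**Disagreement within a pair.** For two disjoint groups with chances a and b it is a(1 − b) + b(1 − a).

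| Split (n) | Events | a | b | Disagree |
|---|---|---|---|---|
| 50/50 (115/115) | 92/92 | 60.9% | 60.9% | 47.6% |
| 60/40 (138/92) | 110.4/73.6 | 67.7% | 52.9% | 49.0% |
| 70/30 (161/69) | 128.8/55.2 | 73.5% | 43.8% | 52.9% |
| 80/20 (184/46) | 147.2/36.8 | 78.4% | 33.4% | 59.4% |

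Simulated Cox fits (4000 trials per split, HR 1 in both groups) gave 47.5%, 53.6% and 59.6% at 50/50, 70/30 and 80/20. In the same simulated trials a two-sided 5% interaction test signalled a difference in 4.2%, 4.8% and 5.3%.

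**Sensitivity.**
- Common true HR, splits 50/50 to 80/20: 36–55% at HR 1.1, 48–53% at 0.9, 39–41% at 0.83, 23% at 0.75 and 9.5% at 0.67.
- Event rate 60% to 90%, at 50/50 and HR 1: 45–50%.
- 189 patients instead of 230, HR 1: 49.7% (50/50) to 58.7% (80/20).
- A diagnosis pair that leaves some patients out (50% and 30% of the trial), HR 1: 51%.

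**What an interaction test could detect.** The standard error of the log ratio of HRs is √(4/E₁ + 4/E₂). For 80% power at two-sided 5%, multiply by 1.960 + 0.842 = 2.802.
- 50/50: √(8/92) = 0.295; exp(2.802 × 0.295) ≈ 2.3.
- 80/20: √(4/147.2 + 4/36.8) = 0.369; exp(2.802 × 0.369) ≈ 2.8.

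**The case against.** The subgroups are labelled secondary, Table 10.1 tests the one-year composite only in ITT and PP, and section 9.1 draws a conclusion only when the test is significant. Section 7.6 also says an analysis will not be attempted if, for instance, the sample is too small. For the one-year composite, the explicit subgroup test rests on the Figure 5 caption, because the one-year block of Table 11.1 does not list that endpoint. All of this stands and limits the weight of the point. None of it supplies a test of whether the effect differs, and the small-sample clause has no threshold.

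The pairs are also not strict complements. COPD without verifying spirometry falls in neither diagnosis group, and a patient admitted on saturation alone may fall in neither hypoxemia group. The derived variables admit emphysema to subgroup 3 and define subgroup 4 as any primary diagnosis other than COPD. Table 6.1 lists emphysema separately, so such a patient can meet both definitions. Incompleteness barely moves the result; the effect of overlap was not calculated.

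A reader might infer more than the SAP supports:
- *That paired subgroups disagree about half the time whatever the common effect.* That needs a true HR near 1. HR 1 is the planning value, but the rate falls well below half as the common HR approaches 0.67.
- *That a subgroup failing to exclude 0.67 will be reported as benefiting from 24 h/day.* No text says so, and section 7.5 also reports the HR with its interval and a two-sided p-value for a difference between treatments.
- *That an interaction test would make the separate results agree.* It would not. The disagreement comes from low subgroup power.

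**Conclusion.** The point holds as a weakness in the secondary analyses. The SAP tests each subgroup separately against 0.67 and has no analysis of the contrast that the subgroups are there to examine. At its planning values, paired results would differ in about 48% to 59% of trials in which the effect is the same in both groups. This rests on assumed splits of 50/50 to 80/20, on treating the two groups as disjoint, and on a common HR near 1. A split result would therefore say little about effect modification. The primary conclusion, drawn from all randomized participants, does not change.

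**What to change.** For the primary endpoint, in the ITT Cox model:
1. Add a treatment-by-hypoxemia term (PaO2 below 7.4 against 7.4 to 8.0 kPa) among patients with a PaO2 on air.
2. In a separate model, add a treatment-by-diagnosis term with mutually exclusive categories. This first requires reconciling emphysema between subgroups 3 and 4 and assigning COPD without verifying spirometry.
3. Report the ratio of HRs with its confidence interval and the interaction p-value.
4. In Figure 5, keep subgroup HRs with 90% intervals, drop the subgroup 0.67 p-values, and state that subgroup results are not separate non-superiority conclusions. The statement is needed because a 90% lower limit above 0.67 is the same test, and a reader can still see it.

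The cost is two models, one clarified definition and a shell edit; no new data are needed. The downside should be written into the SAP: with about 184 events the interaction test has 80% power only for a ratio of HRs of about 2.3 (50/50) to 2.8 (80/20), so a non-significant result does not show a uniform effect.

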7.1 Study conduct and Subject/Patient disposition

Recruitment between sites and over time will be presented. A figure with number of patients included over time will be constructed. Inclusion will also be described as Kaplan-Meier plots of patients randomized per calendar month, first and last inclusion date, descriptive statistics of time from randomization to death or censoring, and number of patients by randomizing centre, for the ITT, PP and **subgroup** populations. (*Table 4 and 5*) (*Figure 1 and 2*)

The number of patients screened and randomized in the study will be presented together with the number of patients completed the study. The numbers withdrawn in total and for each pre-defined withdrawal reason will be presented. The number of LTOT discontinued patients will be presented separately. The allocation of patients to each analysis population group will also be presented together with the reasons for exclusions from Analysis sets. If applicable, a table with number of protocol deviations by category will be created. Number of patients will be presented by treatment and in total. Screening failures (and reasons) will be presented in a listing.

(*Table 1,2 and 3*)

CONSORT flow chart (will be presented as table)

* A patient is correctly randomized if he or she fulfills the inclusion criteria but not the exclusion criteria, has signed informed consent and has been randomized in Swedevox within four weeks of starting LTOT.

**All registry data available except for withdrawals

7.2 Baseline characteristics

Baseline characteristics will be described by randomized treatment and in total for the ITT, PP and subgroup populations. Categorical data will be described as total number and percentage, with missing data as a separate category. Numerical data will be described using number of patients with data, and median, IQR, arithmetic mean and standard deviation for patients with data.

The randomized treatment groups will be compared using the chi-square test statistic for categorical variables and the Wilcoxon's test statistic for numerical data, using observed cases. The results will be presented as p-values, but are not to be considered as statistical tests. They will only be used if needed to satisfy a non-CONSORT journal house style that requires Table 1 p-values. All perceived differences will be due to chance since the groups are randomized.

(Table 6)

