6.2 Per protocol (PP) population

A randomized patient will be excluded from the PP set if LTOT has been discontinued or the mean LTOT utilization during follow-up to the primary endpoint is below 20 h/day for the 24 h/day group, and below 13 h/day or above 17 h/day in the LTOT 15 h/day group. Self-reported oxygen utilization at 12 months, or if that is unavailable, at 3 months will be used for PP classification.

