7.5 Analysis of primary variable

The primary endpoint of the composite event of death or 1st hospitalization at 1 year (day 365; day 0 being the day of randomization) is analyzed with Cox's proportional hazards model. Proportional hazard assumption will be investigated using graphical diagnostics based on the Schoenfeld residuals. The results will be presented as the hazard ratio (HR) for LTOT 24h/day vs. 15h/day with 90% two-sided

confidence interval and the one-sided p-value for the hypothesis test if the lower limit exceeds 0.67 (see section 9.1) A two-sided p-value for the difference between treatments will also be presented. (OS table 10 and table 11). The ITT population will be used for primary analysis but all endpoints will be analyzed according to both the ITT and the Per Protocol (PP) principle.

Statistical significance is defined as a p-value < 0.05. As a sensitivity analysis, the primary analysis is repeated adjusting for sex and age at randomization in years. A frailty model will be performed with “center” as a random effect to account for the clustering by hospital.

Cases withdrawing from LTOT treatment are for the primary analysis handled as

- 1) Per protocol, if it is due to improved oxygenation.
- 2) Having reached endpoint, if it is due to adverse event (such as excessive nose bleeding etc.).
- 3) Censored, if it is due to cancellation of treatment for reasons other than treatment allocation or adverse events (such as starting to smoke etc.).

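### SAP 7.2 ascribes all baseline differences to chance, which is not true of the per-protocol set it also covers; the PP hazard ratio lacks adjustment for severity and can be biased in either direction

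*SAP*

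**What the plan says.** Section 7.2 describes baseline characteristics "by randomized treatment and in total for the ITT, PP and subgroup populations"; Table 6.2 of the output shells is the PP version. P-values between arms may be shown if a journal insists, and the section closes with "All perceived differences will be due to chance since the groups are randomized". It makes no exception for PP.

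Section 6.2 removes a patient from PP if LTOT was discontinued, or if mean use "is below 20 h/day for the 24 h/day group, and below 13 h/day or above 17 h/day in the LTOT 15 h/day group". Hours come from the 12-month questionnaire or, failing that, the 3-month one.

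Section 6 explains why PP is there: non-adherence may pull the arms together, in which case ITT is not the cautious choice. Every endpoint is therefore analyzed both ways. Section 7.5 makes ITT primary. Its Cox model contains treatment only; as a sensitivity analysis "the primary analysis is repeated adjusting for sex and age at randomization in years", and there is a frailty model for center. Table 10.2 mirrors Table 10.1, so a PP estimate adjusted for sex and age is planned. Nothing adjusts for hypoxemia, performance status or diagnosis.

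**The concern.** Randomization makes baseline differences a matter of chance among those randomized. It gives no such assurance for a subset chosen by behavior after randomization, and less still when the rule differs by arm. A patient using 21 h/day stays in PP if allocated to 24 h and leaves it if allocated to 15 h. Any baseline factor linked to hours of use can then be distributed differently in the two PP arms.

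What is at stake is how the PP result is read. Section 6 offers PP as the check on an ITT result that might favor non-superiority too easily. If sicker patients use more oxygen, selection raises the PP hazard ratio for 24 h versus 15 h, which is also the direction that favors non-superiority. ITT and PP could then agree for the wrong reason, and section 7.2 would tell the reader to dismiss the imbalance in Table 6.2 that might reveal it.

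**Working it through.** **1. The plan's own figure.** "The null hypothesis is rejected if the hazard ratio (HR) of continuous oxygen vs. 15h/day exceeds the limit 0.67", with "a one-sided type I error rate of 0.05" and "an event rate of 80% based on Swedevox registry data". Section 9.2 inverts the limit to 1.5 and uses 80% power:

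n = [(1.645 + 0.842) / ln 1.5]² / (0.5 × 0.5 × 0.8) = 188.03, rounded up to 189. This reproduces. The planned size is 230, so the allowance for PP loss is 1 − 189/230 = 17.8%. The sample size is not in dispute.

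**2. Effect of unequal composition.** Suppose severe patients have r times the hazard and make up fractions p24 and p15 of the PP arms. Then, at the start of follow-up,

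apparent HR = true HR × [1 + (r − 1)p24] / [1 + (r − 1)p15].

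With r = 2 and a true HR of 0.67:
- 55% versus 45% severe: 0.67 × 1.55/1.45 = 0.72
- 40% versus 60% severe: 0.67 × 1.40/1.60 = 0.59

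Modest imbalance moves the estimate, and its sign decides the direction.

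**3. How much imbalance the windows can create.** The inputs here are assumptions, since the SAP gives none. Hours are normal with mean 22 in the 24 h arm and 15 to 16 in the 15 h arm. A common SD is chosen so that total PP loss equals 17.8%. Severity raises the log hazard by β = 0.4 to 0.6 per SD, and its correlation with hours is ρ = 0.2 to 0.4. With φ and Φ the normal density and distribution function, the mean standardized hours among those kept are:
- 24 h arm: φ(a)/[1 − Φ(a)], with a = (20 − 22)/SD
- 15 h arm: [φ(l) − φ(u)]/[Φ(u) − Φ(l)], with l = (13 − mean)/SD and u = (17 − mean)/SD

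With Δ the first minus the second, the first-order bias factor on the HR is exp(βρΔ).

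| 15 h mean | SD | kept, 24 h / 15 h | Δ | factor at β 0.4, ρ 0.2 | factor at β 0.6, ρ 0.4 |
|---|---|---|---|---|---|
| 15 | 1.69 | 88% / 76% | 0.225 − 0 = 0.225 | 1.02 | 1.06 |
| 16 | 1.47 | 91% / 73% | 0.174 + 0.365 = 0.539 | 1.04 | 1.14 |

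Reversing the sign of ρ inverts the factors: 1/1.06 = 0.95 and 1/1.14 = 0.88 in the last column. With ρ = 0 there is no selection bias.

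**4. Full follow-up.** The first-order factor overstates the upper end, because high-risk patients leave the risk set early when 80% have events. Simulating the Cox model over these inputs gives:
- no true effect: PP HR about 1.02 to 1.11
- conditional HR of 0.67: PP rejects HR ≤ 0.67 in about 8% to 26% of trials
- same scenarios, ITT: about 6% to 12%

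ITT exceeds 5% because omitting a prognostic factor pulls the marginal HR toward 1 (about 0.69 to 0.72). The selection effect is the excess of PP over ITT, not over 5%.

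**5. Other hour distributions.** With means 21.5 and 15.5 and SDs 2.5 and 2.0 (about 30% lost from PP), severity HR 1.6 per SD and a true HR of 0.67, correlations of 0, 0.3 and 0.5 give PP HRs of 0.69, 0.75 and 0.79 and rejection rates of 6.8%, 14.5% and 22.5%. At a correlation of −0.5, with severity HR 1.3 to 2.0, the PP HR is 0.59 to 0.62 and the rate 1% to 2%. Adjusting for the severity variable returns 0.66 to 0.67. That last result is by construction, since severity is the only confounder in the model.

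**The case against.** The strongest reply is that the sentence carries little weight. It accompanies p-values that the SAP says are not tests, and no model or decision depends on it. A reader might infer that the plan calls the PP effect estimate randomized; it nowhere does. It also plans the means of seeing selection: PP baseline by arm in Table 6.2 and exclusion reasons by arm in Table 2. This stands, and it limits the wording point. It does not supply an estimate that accounts for severity.

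A reader might also take the 8% to 26% as the trial's type I error. The documents do not support that: ITT is primary, the conclusion in section 9.1 follows the primary test, and no rule lets PP confirm or overturn it.

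Nor do the documents show that the PP hazard ratio is in fact biased toward non-superiority. They give no relation between severity and hours. The 15 h window also drops users below 13 h/day and is symmetric about 15, so if use centers on 15 that arm contributes no selection (first row of the table). Larger effects come from wider spreads of hours. Means of 22 and 16 with SD 3 give a null PP HR of 1.06 to 1.15 but exclude 39% of patients, more than twice the planned allowance.

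Finally, elaborate weighting would be fragile. Arm-specific weights on eight or more factors, with no imputation, are too much for one PP arm of this size (76% of 115 is about 87 patients in the 15 h arm).

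**Conclusion.** The section 7.2 statement is wrong for the PP set, and the planned PP hazard ratio has no control for baseline severity beyond sex and age. The possible bias is moderate. With inputs consistent with the 18% allowance and a positive severity-hours correlation of 0.2 to 0.4, a null PP HR moves to about 1.02 to 1.11, and PP rejection at a conditional HR of 0.67 is about 8% to 26% against 6% to 12% for ITT. A negative correlation reverses the direction and zero removes the bias. Severity effect, correlation and hour distributions are all assumed. The finding concerns the supporting analysis that section 6 offers as a safeguard and leaves the formal error rate of the primary ITT test untouched.

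**What to change.** - In section 7.2, restrict the due-to-chance sentence to the randomized (ITT) comparison, and state that imbalance in Table 6.2 will be read as possible selection.
- In section 7.5 and Table 10, pre-specify beside the unadjusted PP result a PP Cox model adjusted for a small set of baseline factors already in Swedevox: age, sex, PaO₂ on air, WHO performance status and primary diagnosis. Inverse-probability weighting on the same small set is an optional alternative.
- Settle this before unblinding, because section 6 has patients classified into analysis sets after the analyst is unblinded.

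The cost is some wording and one extra model. With about 189 PP patients and 80% events there would be roughly 189 × 0.8 = 151 events. If performance status enters as a score and diagnosis as COPD versus other, that is five coefficients, or about 30 events each. Patients with missing covariates drop out of this model because no imputation is planned. Selection through post-baseline events, questionnaire response or unmeasured factors remains, so the adjusted PP result removes only the measured part of the bias.
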